## **9.4 Demographics, baseline characteristics and concomitant medications**

Descriptive statistics will be applied to demographics, baseline characteristics, concomitant medication, and medical history by group (fasted/fed) and total population.

Medical history will be coded according to the current version of MedDRA at the time of start of the trial, and concomitant medication will be coded with the WHO Drug Dictionary.

## **9.5 Treatment compliance**

Dose and time of dosing will be listed by participant.

## **9.6 PK analyses**

Pharmacokinetic parameters of AEF0117, including  $C_{\max}$ ,  $C_{\min,24h}$ ,  $C_{\text{last}}$ ,  $T_{\max}$ ,  $T_{\text{lag}}$ ,  $t_{1/2}$ ,  $AUC_{0-t}$ ,  $AUC_{0-\infty}$ , % $AUC_{\text{extrap}}$ ,  $CL/F$  and  $Vd/F$  will be calculated using non-compartmental methods and summarized by graphic displays and descriptive statistics as data permit.

### **9.6.1 Primary endpoint**

The primary analysis will be based on a comparison of the ratio between fed and fasting condition for the following parameters: the mean  $C_{\max}$ ,  $AUC_{0-t}$ , and  $AUC_{0-\infty}$  of each group. Descriptive statistics will be applied to  $T_{\max}$  and  $T_{\text{lag}}$ .

PK analysis will consist of a non-compartmental evaluation of AEF0117 plasma concentration-time profiles to determinate PK parameters using a validated program. PK parameters will be tabulated and summarized using descriptive statistics (mean, median, SD, geometric mean, CV%, minimum, and maximum).

The relative bioavailability will be estimated by calculating the ratio of the geometric means between fed and fasted conditions, based on log-transformed data, for  $AUC_{0-t}$ ,  $AUC_{0-\infty}$  (when appropriate) and  $C_{\max}$ . The 90% CI will be provided. The clinical relevance of any differences between fed and fasted conditions will be discussed, especially with respect to an assessment of the CI in relation to the limits.

An analysis of variance model will be applied, with sequence, period, and state (fed, fasting) as factors.

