## 1 PROTOCOL SUMMARY

### 1.1 Protocol synopsis

Trial title	The effect of food on the oral bioavailability of AEF0117 in healthy volunteers.
Signatory investigator	[name]
Trial site	New York State Psychiatric Institute (NYSPI), Columbia University
Clinical phase	1
Objectives	
Primary objective
 

• To determine the bioavailability of orally administered AEF0117 after fed conditions relative to fasting conditions in healthy volunteers.

 
Secondary objectives
 

• To evaluate other pharmacokinetic (PK) parameters of AEF0117 in healthy volunteers.

• To evaluate safety and tolerability of a single dose of 1 mg AEF0117 in healthy volunteers.

 
Exploratory objective
 

• To characterize potential metabolites regarding plasma PK.

Trial design	
This is a single center, randomized, parallel-group, 2-arm, open-label, single-dose trial in healthy male and female volunteers aged 18–55 years, both inclusive.
 
The total trial duration for an individual participant will be up to 6 weeks (42 days) from screening (up to 28 days prior to dosing) to the final follow-up visit (14 days after dosing).
 
After screening, the trial includes 2 days where the participants are confined at the research facility, and thereafter 7 visits to the site (6 visits and a follow-up visit). Participants will stay in the research facility from the afternoon prior to dosing on Day 1 and until collection of the blood sample 24 hours after dosing (i.e., Day 2) and then be discharged. Participants will be asked to return to the research facility for collection of blood samples each morning on Days 3, 4, 5, 7, 9, and 11, and at the follow-up visit on Day 14.
 
On Day 1, eligible participants will be randomized and receive a single dose of 1 mg AEF0117 in fed or fasting condition, and serial blood samples will be collected up to 312 hours after dose administration.

Number of participants	A total of 32 participants will be randomized 1:1, stratified by sex, into 2 groups. One group of 16 participants will be dosed after fasting for 10 hours, while the other group of 16 participants will be dosed 30 minutes after start of consumption of a standardized high fat breakfast (US Food and Drug Administration [FDA] breakfast).

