### 4 TRIAL DESIGN

#### 4.1 Overview

This is a single center, randomized, parallel-group, 2-arm, open-label, single-dose trial in healthy male and female volunteers aged 18–55 years to obtain data on the effect of food on the oral bioavailability of AEF0117.

A total of 32 healthy volunteers are planned to be enrolled. Participants will be randomized in a 1:1 ratio to receive 1 dose of AEF0117 1 mg in fasted condition (16 participants) or fed condition (16 participants). The participants will be divided into smaller cohorts of minimum 2 participants for operational reasons (adjusted to capacity of the research facility) and each cohort will include 1 fasting participant and 1 participant receiving breakfast prior to dosing.

The total trial duration for an individual participant will be up to 6 weeks (42 days) from screening (up to 28 days prior to dosing) to the final follow-up visit (14 days after dosing).

After screening, the trial includes 2 days where the participants are confined at the research facility, and thereafter 7 visits to the site (6 visits and a follow-up visit). Participants will stay in the research facility from the afternoon prior to dosing on Day 1 and until after collection of the blood sample 24 hours after dosing (i.e., Day 2) and then be discharged.

Participants will be admitted to the research facility during the afternoon on Day -1 where it will be verified that the participants are still eligible according to the inclusion and exclusion criteria,

and the baseline assessments will be performed. After an overnight stay in the research facility, participants will be randomized to fasted or fed state and dosed with a single oral dose of 1 mg AEF0117.

Blood samples for determination of AEF0117 and potential metabolites of AEF0117 in plasma will be collected before dosing and repeatedly for up to 2 weeks after dosing.

Safety will be monitored throughout the trial by assessment of AEs, suicidal risk, clinical safety laboratory parameters, pregnancy tests (females only), vital signs, ECGs, and physical examinations.

The schedule of activities summarizing all procedures is provided in section 1.3, and a description of procedures by visit is provided in section 8.1.

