## 4.2 Scientific rationale for the trial design

### 4.2.1 Justification for design and parameters

This trial will examine the effects of food on AEF0117 bioavailability in healthy volunteers. Standard PK parameters will be calculated, and a high fat meal will be served according to current guidance [10].

A parallel-group design has been chosen since detectable plasma concentration has been observed 2 weeks after discontinuation of multiple dosing of 1 mg/day due to the long elimination half-life of AEF0117 in humans. A crossover design would have required a long washout period with a potential risk of a high dropout rate.

As AEF0117 is a lipophilic compound it is anticipated that intake of a high fat meal will introduce a slight food effect i.e., increase the bioavailability, and the trial has been powered for such an effect. A total of 32 participants will be randomized 1:1 to fed or fasted conditions with an aim to complete 14 in each group. In alignment with FDA guidance [10, 11], at least 12 participants will complete the 72-hour PK sample in each group.

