### 4.2.2 Justification for dose and route

AEF0117 is formulated as a soft capsule for oral administration. In this parallel-group food-effect bioavailability trial, a single dose will be administered to each participant.

The 1 mg dose has been selected since it is considered the highest therapeutic dose and has been shown to reduce the abuse-related subjective effects of cannabis and its self-administration in a phase 2a trial. Once daily administration of 1 mg dose for 5 days in patients with CUD has shown good safety and tolerability. In healthy volunteers, multiple dosing of up to 6 mg once daily for 7 days was considered safe and well tolerated with no SAEs, and only 2 moderate and no severe TEAEs.

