### **6.3 Participant identification and assignment to trial intervention**

All participants will be assigned a unique trial participant number at the trial-specific screening.

A computer-generated randomization schedule will be prepared by a statistician. Eligible participants will be randomly assigned to 1 of the 2 groups. Randomization will be with a block size of 2 and stratified by sex.

The 2 groups will be divided into smaller cohorts of at least 2 participants for operational reasons (adjusted to in clinic facilities) and each cohort will include a similar number of participants from each group (fed or fasting).

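### The primary analysis is specified as a crossover ANOVA (sequence, period, state) although the trial has one period and parallel groups; the stratification factor sex is left out

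*Protocol*

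**What the plan says.** **Model.** Section 9.6.1 of the protocol says: "An analysis of variance model will be applied, with sequence, period, and state (fed, fasting) as factors". The statistical methods part of the synopsis (section 1.1) repeats the sentence. No section defines sequence or period for this trial, and none gives another primary model.

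**Design.** Section 4.1 describes a "single center, randomized, parallel-group, 2-arm, open-label, single-dose trial". Section 4.2.2 adds: "In this parallel-group food-effect bioavailability trial, a single dose will be administered to each participant". Section 4.2.1 gives the reason, which is the long half-life: "A parallel-group design has been chosen since detectable plasma concentration has been observed 2 weeks after discontinuation". It also explains why the alternative was not used: "A crossover design would have required a long washout period with a potential risk of a high dropout rate".

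**Randomization.** Section 6.3: "Randomization will be with a block size of 2 and stratified by sex". The synopsis agrees: "A total of 32 participants will be randomized 1:1, stratified by sex, into 2 groups".

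**Target of the analysis.** Section 9.6.1 asks for the fed/fasted ratio of geometric means from log-transformed data, with a 90% CI, for Cmax, AUC0-t and (when appropriate) AUC0-∞.

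**The concern.** Sequence and period are the factors of a two-period crossover, in which each participant is observed under both conditions in a randomized order. Here each participant contributes one value per PK parameter, so neither factor exists as something distinct from the intercept or the randomized group.

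This sentence governs the primary ratio and its 90% CI. Taken literally, it gives no separate fed/fasting estimate, or it leaves the software to decide which of two identical terms to drop. Whoever runs the analysis must depart from the stated model, and section 9.3 requires departures from planned analyses to be described and justified in the trial report. That is an avoidable deviation on the primary endpoint.

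The model also omits sex, the only stratification factor. In a parallel-group trial all between-participant variation falls into the error term. If sex affects exposure materially, leaving it out makes the interval wider than it need be.

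**Working it through.** **Inputs.** From section 9.1: CV 0.3, true ratio 1.25, upper limit 1.75 for the 2-sided 90% CI, 14 or 12 participants per group. From the synopsis and section 4.1: 16 + 16 participants, one dose each. From section 6.3: stratification by sex.

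**1. Which analysis does the sample size assume?**
- Log-scale SD = √ln(1 + 0.3²) = 0.2936.
- Distance to the limit = ln(1.75) − ln(1.25) = 0.3365.
- Standard error of the difference in log means = 0.2936 × √(2/n), which is 0.1110 for n = 14 and 0.1198 for n = 12.
- Noncentrality = 0.3365/0.1110 = 3.03 and 0.3365/0.1198 = 2.81.
- Power from the noncentral t, one-sided 5%, 2n − 2 degrees of freedom:

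| Reading | 14 | 12 |
|---|---|---|
| Protocol | 90% | 86% |
| Two independent groups, n per group | 90.4% | 85.9% |
| 2×2 crossover, 2n participants (28, 24) | 99.4% | 98.6% |
| 2×2 crossover, n participants in total | 88.7% | 83.3% |

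The crossover rows treat 0.3 as a within-participant CV. The two-group reading fits best, so the power calculation matches the parallel design and not the written model.

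**2. Can the written model be fitted?** Take 32 participants with one observation each and the columns intercept, sequence, period and state.
- Period has one level, so its column equals the intercept.
- If sequence is the assigned condition, its column equals state. The matrix has rank 2 for 4 columns, and the state contrast is not estimable.
- If sequence is a constant, the rank is again 2. State is then estimable, but only because two of the three stated factors have vanished and a one-way comparison remains.
- With intercept, sex and state, the rank is 3 for 3 columns and state is estimable.

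**3. Precision of the two-group analysis.** At 14 per group (26 df) the 90% CI factor is exp(1.706 × 0.1110) = 1.208. At an observed ratio of 1.25 the interval is 1.25/1.208 = 1.03 to 1.25 × 1.208 = 1.51.

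**4. Effect of adding sex.** Residual degrees of freedom at 14 per group fall from 26 to 25. If sex explains a share R² of log-scale variance, the SD becomes 0.2936 × √(1 − R²). The protocol gives no R², so these values are assumed:

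| R² for sex | Power, 14 per group |
|---|---|
| 0 | 90.4% |
| 5% | 91.6% |
| 10% | 92.8% |
| 20% | 95.1% |

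At 12 per group with R² = 0, power is 85.8% against 85.9% without sex.

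The 90.4% baseline is the ordinary two-group formula, which gives no credit for stratified allocation. Simulating trials with 14 per group, seven of each sex in each group, and sex left out of the model gives about 91.0, 91.4 and 92.4% power for R² of 5, 10 and 20%. The part of the gain due to the model term alone is therefore about 0.6, 1.4 and 2.7 points. In the same simulations the unadjusted nominal 90% interval covers about 91.0, 91.7 and 93.5%, so it is conservative.

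**The case against.** The strongest reply is that this is leftover crossover wording with no numerical effect. If sequence and state are the same column, dropping either one leaves the same fitted group difference, residual variance and interval. If both spurious factors are treated as single-level, an ordinary one-way comparison remains. Section 9.6.1 separately defines the ratio of geometric means, and section 9.1 is powered for two groups, so the intention is clear and a programmer would notice the problem.

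This is correct as far as it goes. A valid two-group contrast can be recovered, and sample size, power and expected interval do not change. But it is recovered only by abandoning the stated model. Nor can the point be left to the SAP: the protocol positively states a wrong model, twice, and section 9.3 says the SAP elaborates the analyses outlined there. The SAP would have to repeat the error or contradict the protocol.

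On sex, the reply is that covariates are commonly settled in the SAP, that omission does not bias the ratio because allocation is balanced within sex, that no section supports a sex effect on exposure, and that a negligible effect would not repay the lost degree of freedom. All of this stands. It makes sex a matter of precision and of consistency with the randomization, secondary to the model error.

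Dosing cohorts are also a design feature (sections 4.1 and 6.3), so sex is not the only one. They are operational, however. At the minimum size of 2 there would be 32/2 = 16 of them, costing 15 degrees of freedom, and they are not a stratification factor.

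**Conclusion.** The point holds. The primary model contradicts the design in sections 4.1, 4.2.1 and 4.2.2 and the power calculation in section 9.1, and it cannot be fitted as specified: rank 2 for 4 columns. Non-estimability of the fed effect is exact when sequence is coded as the assigned condition; under the other coding two of the three factors do not exist. Either way the text must be corrected before data are seen, because it governs the primary result.

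The error does not threaten the trial's size or validity. The two-group analysis has 90.4% and 85.9% power at 14 and 12 per group under the protocol's own assumptions. Leaving out sex causes no bias. Its cost in precision depends on an unknown sex effect and is small unless that effect is material.

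**What to change.** In section 9.6.1 and in the synopsis, delete sequence and period and replace the sentence with wording such as:

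> Log-transformed Cmax, AUC0-t and AUC0-∞ will be analysed by a linear model with condition (fed, fasting) and sex (the stratification factor) as fixed factors. The back-transformed difference in least-squares means and its 90% CI give the fed/fasting ratio.

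Use the same model in the SAP. The cost is one sentence in two places of the protocol, matching SAP wording and 1 residual degree of freedom. The planned 32 participants and the stated power need no change.

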## 9.6.2 Secondary endpoints

Additional PK parameters of AEF0117, including  $C_{min,24h}$ ,  $t_{1/2}$ , %AUCextrap, CL/F, and Vd/F will be calculated using non-compartmental methods and summarized by graphic displays and descriptive statistics as data permit. Individual and summary (means  $\pm$  SD for each condition i.e., fed/fasting) plasma AEF0117 concentration-time plots will be displayed graphically.

## 9.7 Safety analyses

### 9.7.1 Drug exposure

Drug exposure (dosing) will be summarized descriptively for the safety data population.

### 9.7.2 Adverse events

An AE with onset after administration of trial drug is considered treatment emergent.

AEs will be summarized by MedDRA SOC and PT. AE summary tables will include the number of participants reporting an AE (n), the percentage of participants with an AE (%), and the number of events reported (E). AEs will be presented by group (fasted/fed) and the total population.

The incidence of treatment-related AEs and not related AEs will be tabulated. If the investigator does not specify the relationship of the AE to trial drug the AE will be considered treatment related. AEs will also be summarized by severity (mild, moderate, severe). If the severity is missing, the AE will be regarded as severe. An AE that increases in severity over time will for the purpose of analysis be considered as one AE with the maximum intensity recorded.

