### **7.3.2 Time period and frequency for collection of adverse event and serious adverse event**

All AEs will be collected in this trial at each visit starting after the informed consent for trial participation has been signed and until the follow-up visit (Day 14).

Signs and symptoms present prior to dosing of the trial drug that would qualify as an AE if presented later, should be recorded as AEs in the eCRF with date/time of occurrence, to be able to evaluate any increase in severity during treatment, and will be designated pre-treatment-emergent AEs. AEs that are not present at baseline, or if present at baseline, have worsened in severity after dosing of AEF0117 on Day 1 will be considered treatment-emergent AEs (TEAEs).

The investigator is not obligated to actively seek information on AEs or SAEs after a participant has concluded trial participation. However, if the investigator detects an SAE in a trial participant after the end of the period of observation, and considers the event possibly related to prior trial treatment, he/she should promptly contact the sponsor to determine how the event should be documented and reported.

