#### **7.3.4.2 Intensity/severity of the adverse event**

The severity of an AE will be graded according to the scale below. The severity of the AE is determined by the principal investigator, who may consult with the sponsor’s medical monitor, if needed.

- *Mild*: A sign or symptom that do not disrupt usual activity.
- *Moderate*: A sign or symptom with sufficient intensity to affect usual activity (disturbing).

- *Severe*: A sign or symptom resulting in considerable interference with the participant's daily activities (unacceptable).

When the intensity of an AE worsens over time for a reporting period (e.g., between visits, etc.), each increase in intensity will be reported as a new AE until the event resolves.

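### Section 9.7.2 omits the worsening limb of the section 7.3.2 definition, so a pre-dose AE that worsens after dosing can be classified as not treatment emergent

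*Protocol*

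**What the plan says.** Four statements in the protocol bear on this point.

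- **Section 7.3.2 (AE collection)** gives a TEAE two limbs. The first is an AE absent at baseline. The second covers AEs that, "if present at baseline, have worsened in severity after dosing of AEF0117 on Day 1 will be considered treatment-emergent AEs (TEAEs". The same section has pre-dose signs and symptoms recorded "to be able to evaluate any increase in severity during treatment, and will be designated pre-treatment-emergent AEs".
- **Section 7.3.4.2 (severity)** says that, when an AE worsens over a reporting period, "each increase in intensity will be reported as a new AE until the event resolves".
- **Section 9.7.2 (AE analysis)** opens with "An AE with onset after administration of trial drug is considered treatment emergent". Section 9 contains no other statement of what counts as treatment emergent.
- **Section 9.7.2** closes with "An AE that increases in severity over time will for the purpose of analysis be considered as one AE with the maximum intensity recorded".

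On output, section 9.7.2 says "AEs will be summarized by MedDRA SOC and PT" and adds breakdowns by relationship and severity. It names no table restricted to TEAEs.

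**The concern.** The section that governs the analysis uses a narrower definition than the section that governs collection. The omitted limb is the one for which pre-dose events are recorded in the first place.

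Safety and tolerability is a secondary objective, with AEs among its endpoints (section 3). AEs are collected from consent, and screening can begin on Day -28, so the pre-dose window can be longer than the 14 days of follow-up. Before dosing, participants give up caffeinated drinks (section 6.7.3), have a catheter placed (section 7.2.1) and fast overnight (section 8.1.2). Headache is among the AEs seen in two or more participants in the earlier studies (section 2.3.1). A headache that is present before dosing and worse afterwards is therefore a realistic case. If it is classed as not treatment emergent, the post-dose worsening is missed by any count built on that classification.

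**Working it through.** The protocol states no figure to reproduce. The check is a comparison of rules, followed by simple arithmetic for scale.

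**Step 1. The two definitions.**

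| Situation | Section 7.3.2 | Section 9.7.2, first sentence |
|---|---|---|
| AE starts after dosing | TEAE | TEAE |
| AE present before dosing, worsens after dosing | TEAE | not covered |
| AE present before dosing, does not worsen | not a TEAE | not covered |

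The sections differ in the second row. Section 9.7.2 gives no basis for separating the second row from the third.

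**Step 2. Does the recording rule close the gap?** Under section 7.3.4.2 the worsening is a new AE record. If that record carries its own post-dose start time, it meets the section 9.7.2 sentence. Taken alone, this would bring the second row back into line with section 7.3.2.

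**Step 3. What does the merging rule do?** Section 9.7.2 then treats the records of a worsening AE as one AE. It fixes the intensity of the merged AE (the maximum) but not its onset.

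**Step 4. Worked case.** A mild AE starts on Day -1 and becomes moderate 2 hours after dosing.

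- Section 7.3.2: 1 TEAE.
- Section 9.7.2, merged AE keeps its first onset (the natural reading, since it is one AE that began before dosing): 0 TEAEs.
- Section 9.7.2, the onset of the worsening record is used: 1 TEAE.

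Two programmers could follow section 9.7.2 faithfully and obtain different counts from the same data.

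**Step 5. Scale.** Section 4.1 plans "1 dose of AEF0117 1 mg in fasted condition (16 participants) or fed condition (16 participants"), so n = 16 per arm and 32 in total. For k affected participants with no other TEAE, the shift in the proportion with at least one TEAE is k/n:

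- one participant, within an arm: 1/16 = 6.25 percentage points;
- one participant, overall: 1/32 = 3.1 percentage points.

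The protocol gives no value for k. If k is assumed to lie between 1 and 3, the overall shift is between 1/32 = 3.1 and 3/32 = 9.4 points. For an affected participant who has another TEAE, the shift in this proportion is zero.

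**The case against.** The case against has several parts.

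- **The sentence states a sufficient condition.** Section 9.7.2 does not say that only AEs with onset after dosing are treatment emergent, and it could be read together with section 7.3.2. This stands as far as it goes: exclusivity is an inference. But the sentence is the sole definition in the analysis section and lacks the limb that section 7.3.2 supplies.
- **Worsening is itself a new AE.** Section 7.3.1 counts worsening of an existing condition as an AE, and section 7.3.4.2 records it as a new one. The closing sentence of section 9.7.2 might also be meant only for severity counts. That reading is possible, but the text does not limit the merge in this way, so the ambiguity remains.
- **No TEAE table is named.** A reader might infer that worsening events, even severe ones, drop out of the TEAE tables. The protocol does not support that. Its tables are of AEs, collection starts at consent, section 9.3 has all data listed, and the maximum-intensity rule would show the event at its worst grade. The loss occurs only in output filtered on the treatment-emergent classification.
- **The SAP can settle it.** Section 9.3 has a SAP finalized before the first dose, and the onset of a merged record is a derivation detail that could be left to it. The mismatch between the two stated definitions, however, is in the protocol itself, and the SAP is to elaborate the analyses as section 9 outlines them.
- **The size is assumed.** This stands. Some participants with pre-dose AEs will also never be dosed, under the dosing-day criteria in section 5.3.3.

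**Conclusion.** Section 9.7.2 is wrong as written, in a limited way. It leaves out the worsening limb of section 7.3.2, and its merging rule undercuts the one provision that could have made up for the omission. A post-dose worsening of a pre-dose AE can therefore be classified as not treatment emergent when section 7.3.2 says that it is.

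The effect is confined to that classification and to whatever counts or tables use it. The per-participant shifts above hold only for a participant without another TEAE, and the number of such participants is unknown. Safety reporting here is descriptive, and neither the primary PK analysis nor the sample size depends on the definition.

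**What to change.** Make two changes to section 9.7.2, carried into the SAP:

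1. Replace the opening sentence with the section 7.3.2 definition: an AE is treatment emergent if its onset is after dosing, or if it was present before dosing and worsened in severity after dosing.
2. State that severity records are merged separately before and after dosing, so that a post-dose worsening counts as one TEAE at its maximum post-dose severity.

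The cost is one or two sentences and a small programming change. No new data are needed, because AE start and stop times and severity are already recorded (section 7.3.4). The natural deadline is the first dose, by which section 9.3 requires the SAP to be final.
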